#### 3.3.1.3.2 Replacement of Subjects

Subjects who discontinue from the study within the first 4 weeks will be replaced. However, subjects who discontinue from the study after 4 weeks will not be replaced. If possible, HbA1c measurements will be obtained for subjects who discontinue after 4 weeks of participation.

#### 3.4 STUDY TREATMENT

#### 3.4.1 Test Product, Dose, and Mode of Administration

The test product is defined as Afrezza administered using the inhaler (Table 1). Afrezza consists of single-use plastic cartridges filled with a white powder containing insulin, which is administered via oral inhalation using the Afrezza Inhaler only.

Afrezza Inhalation Powder is a dry powder supplied as 4-, 8-, or 12-unit cartridges.

The Afrezza Inhaler is breath-powered by the subject. When the subject inhales through the device, the powder is aerosolized and delivered to the lung.

**Table 1: Test Product (Afrezza)** 

| Test Product  |  |  |  |  |  |
|---|--|--|--|--|--|
| Afrezza®  |  |  |  |  |  |
| Technosphere® Insulin inhalation powder and Gen2C inhalation system   |  |  |  |  |  |
| MannKind Corporation  |  |  |  |  |  |
| Human insulin, recombinant DNA origin   |  |  |  |  |  |
| Inhalation powder   |  |  |  |  |  |
| Each milligram of formulation contains 3.0 units of human insulin.  |  |  |  |  |  |
| Oral inhalation   |  |  |  |  |  |
| The inhaler is breath-powered by the subject. When the subject inhales through the device, the powder is aerosolized and delivered to the lung. |  |  |  |  |  |
| Individualized  |  |  |  |  |  |
| Refrigerated at 2°C to 8°C (36°F to 46°F): Until expiration date Note: The inhaler should be at room temperature for 10 minutes before use.     |  |  |  |  |  |
|   |  |  |  |  |  |

Confidential Page 30 of 70

| Test Product          |  |  |  |  |  |  |
|-----------------------|--|--|--|--|--|--|
| Storage (In Use)      | 
 
Room temperature storage 25°C (77°F)
 
Excursions permitted to 15 to 30°C (59°F to 86°F)
 
Sealed (unopened) blister card: Must be used within 10 days
 
Opened strip: Must be used within 3 days
 
 |  |  |  |  |  |
| Packaging             | Blister card containing 15 cartridges. Two blister cards are overwrapped in a foil pouch.  |  |  |  |  |  |
| Strength(s)           | Pre-metered single-dose 4-, 8-, and 12-unit cartridges will be provided.   |  |  |  |  |  |
| Lot and Batch Numbers | Will be recorded in the study master file and provided in the final clinical study report  |  |  |  |  |  |

#### 3.4.2 Basal and Rapid-Acting Insulin Therapy Dose and Mode of Administration

Subjects in the Afrezza + Insulin Degludec group will be treated with insulin degludec administered subcutaneously for basal insulin coverage.

Subjects in the Afrezza + AID Control group will be treated with infused rapid-acting: insulin aspart (Novolog® or Fiasp®) or insulin lispro (Humalog®, Admelog®, or Lyumjev®) for basal insulin coverage (insulin pump/AID users). The dose regimen will be individualized.

Subjects in the AID Control group will be treated with infused rapid-acting: insulin aspart (Novolog or Fiasp) or insulin lispro (Humalog, Admelog, or Lyumjev) for basal insulin and prandial/correction insulin coverage (insulin pump/AID users). The dose regimen will be individualized.

#### 3.4.3 Afrezza Training

At Visit 2, subjects in Afrezza groups (Afrezza + Insulin Degludec and Afrezza + AID) will receive Afrezza inhalation training using the BluHale system, which consists of an Afrezza Inhaler, an empty cartridge, and a pressure-sensing jacket that slips onto each inhaler. The jacket is designed for repeated use on multiple inhalers and does not require sterilization between subjects. Therefore, subjects may use the same jacket during training. Empty cartridges will be provided for training and practice. Subjects must demonstrate the ability to adequately perform the inspiratory maneuver utilizing the empty cartridge to continue in the study.

If, in the opinion of the Investigator, a subject cannot adequately perform the inspiratory maneuver after the second repeated training, the subject will be withdrawn from the study.

#### 3.4.4 Dosage Schedule

Subjects in the Afrezza groups (Afrezza + Insulin Degludec and Afrezza + AID) will administer their first dose of Afrezza at Visit 2, at the start of the meal challenge. Afrezza will be dosed at 2 × the calculated RAA dose rounded down to the nearest 4-unit dose (based on their I:CHO dose calculated for mealtime), but not exceeding 24 units of Afrezza. The Afrezza dose will be administered at the start of the meal challenge. The start of the meal will define t=0. After the

Confidential Page 31 of 70

meal challenge and at subsequent visits, Afrezza will be titrated to glycemic effect per Investigator discretion.

Table 2: Starting Dose of Afrezza for Subjects in the Afrezza Groups

| RAA Dose (Units) | Afrezza Dose (Units) |
|------------------|----------------------|
| <4               | 4                    |
| 4                | 8                    |
| 5                |                      |
| 6                | 12                   |
| 7                |                      |
| 8                | 16                   |
| 9                |                      |
| 10               | 20                   |
| 11               |                      |
| ≥12              | 24*                  |

RAA=rapid-acting insulin analog (e.g., insulin aspart or insulin lispro)

Note: Aside from the initial mealtime dose cap mentioned (24 units of Afrezza), there is no maximum dose of Afrezza and the required total mealtime dose for the subject during the study may differ from the examples provided in this table.

Following the initial dose of Afrezza and throughout the study, post-meal insulin correction doses can be taken no sooner than 60 to 90 minutes after a previous dose of Afrezza if the subject's glucose value is >160mg/dL, or per investigator discretion. Subjects in the Afrezza+AID group will correction dose with RAA while subjects in the Afrezza+Tresiba group will correction dose with Afrezza.

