#### 1.2 Study Rationale

Approximately 40% to 60% of patients with T1DM use continuous subcutaneous insulin infusion (CSII) devices, commonly referred to as insulin pumps (Umpierrez et al. 2018, Miller et al. 2015). CSII devices are computerized devices programmed to deliver an RAA under the skin continuously throughout the day via a catheter attached to a person's abdomen. When used in tandem with continuous glucose monitoring (CGM) this is a closed-loop system. Hybrid closed-loop systems are characterized by the coexistence of algorithm-driven automated insulin delivery (AID) for basal insulin coverage combined with manual mealtime bolus insulin doses.

The current study aims to evaluate mealtime use of Afrezza in adults ≥18 years of age with T1DM who currently use AID. In this study, Afrezza-treated subjects will use two different methods for basal insulin delivery (subcutaneous [SC] injection of long-acting insulin or an AID system with RAA) compared to a control group (without Afrezza) of patients on an AID system with RAA.

Subjects will administer their initial Afrezza dose based on the subject's current insulin-to-carbohydrate (I:CHO) ratio multiplied by 2 and rounded down to the nearest Afrezza dose size, subject to Investigator discretion, but not exceeding 24 units of Afrezza. Pooled Afrezza trial data suggests that subjects achieve similar glycemic control with a dose ratio of 1.5- to 2-fold the equivalent unit value of a subcutaneous insulin analog in head-to-head comparisons (Kendall et al. 2020, Grant et al. 2019), which is significantly higher than the dose conversion in the label. Additionally, a proof-of-concept study was done with 20 patients demonstrating improved postprandial glucose excursions (PPGE) with the higher dose of Afrezza compared to the current label (Afrezza 2020). This higher initial conversion dose of Afrezza will be used for the first dose under medical supervision in the clinic.

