- ). The site will de-identify all reports and data. Subjects will undergo a 2-hour meal tolerance test in the clinic. The Afrezza + Insulin Degludec and the Afrezza + AID groups will be administered an Afrezza initial dose that is 2 times the calculated RAA dose (based on their insulin-to-carbohydrate ratio [I:CHO] calculated prandial dose) rounded down to the nearest 4-unit dose of Afrezza, but not exceeding 24 units of Afrezza. The Afrezza dose will be administered at the start of the meal challenge. The AID Control group will administer bolus insulin  $10 \pm 5$  minutes (per label) prior to the meal, per Investigator discretion. The start of the meal will define t=0. Subjects in the Afrezza + Insulin Degludec will continue on AID throughout the meal tolerance test and then transition to insulin degludec at the discretion of the Investigator. Basal insulin doses and time of administration in all study subjects will be documented. Subjects should have glucagon available for use in the event of hypoglycemia and should not be discharged until hypoglycemia is resolved.
- Visits T3, T4, T5, T6, T7, T8 (Telephone): Between Visits 2 and 9 in the clinic, several telephone visits will be conducted. During these visits, the Investigator will titrate insulin dosages, ask about changes to concomitant medications, record any AEs and hypoglycemic events, and answer any questions/concerns raised by the subject.
- Visit 9 (Clinic): This visit will be conducted at least 30 days (+7 days) after Visit 2. CGM reports and pump reports will be downloaded from V2 to V9 and from 10 days prior to V9 to V9 using Carelink for Medtronic CGM and pumps, CGM reports/data and pump reports/data will be downloaded from V2 to V9 and from 10 days prior to V9 to V9 using Clarity for Dexcom CGM and t:connect for Tandem pump). The site will de-identify all reports and data. The Investigator will titrate insulin dosages. Basal insulin dosages will be documented.
- Visits T10, T11, T12 (Telephone): Between Visits 9 and 13 in the clinic, three telephone visits will be conducted. During these visits, the Investigator will titrate dosages and answer any questions/concerns raised by subjects.

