## 3.7.2.1 Meal Challenge

Subjects will come into the clinic in a fasting state for Visit 2, with exception of treating hypoglycemia. Fasting will be defined as no intake of drink or food, with exception of water, for  $\geq$ 6 hours before the clinic visit. Subjects will also be instructed not to administer manual bolus doses of insulin during the 4 hours immediately preceding the meal challenge. If the subject requires a manual bolus insulin dose to correct hyperglycemia within the 4 hours prior to the scheduled visit, the meal challenge will need to be rescheduled.

The CGM glucose value will be confirmed 15 minutes before the start of the meal. If the subject's CGM value is  $\geq$ 70 mg/dL, the subject can start the meal challenge 15 minutes later. If the subject's CGM value is  $\leq$ 70 mg/dL, the Investigator can provide 15 g of fast-acting carbohydrates and reassess the CGM glucose value after 30 minutes and if the subject's new CGM value is  $\geq$ 70 mg/dL, the subject can start the meal challenge 15 minutes later. The CGM value obtained immediately before the start of the meal (defined as t=0) will serve as the baseline glucose value for that visit.

Subjects in the Afrezza groups will receive training on how to use the Afrezza Inhaler using BluHale technology, as well as how to identify and manage any events of hypo and hyperglycemia.

In addition to CGM, subjects will be instructed to take SMBG measurements 15 minutes before the start of the meal, immediately before the start of the meal (t=0), and at 15, 30, 45, 60, 90, and 120 minutes after the start of the meal challenge.

Confidential Page 45 of 70

mannkind

The meal challenge will consist of 1-2 bottles of Boost nutritional shake (1 bottle is approximately 240 calories, 41 g carbohydrate, 10 g protein, and 4 g fat). The meal is to be fully consumed within 15 minutes. Each Afrezza dose will be administered at the start of the meal challenge. The RAA dose will be administered  $10 \pm 5$  minutes (per label) before the start of the meal challenge, per Investigator discretion.

For Afrezza doses exceeding 12 units, inhalations from multiple cartridges are necessary. To achieve the required total mealtime dose, subjects should use a combination of 4-unit, 8-unit, and 12-unit cartridges.

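### Below a calculated RAA dose of 2 U, the written first-dose rule gives 0 units of Afrezza, while Table 2 gives 4 units and Section 3.4.5 has every Afrezza subject treated at Visit 2

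*Protocol*

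**What the plan says.** - **Rule in words.** Section 3.4.4: "Afrezza will be dosed at 2 × the calculated RAA dose rounded down to the nearest 4-unit dose". The RAA dose is individual: "based on their I:CHO dose calculated for mealtime". Section 3.1 has the same step and cap: "rounded down to the nearest 4-unit dose of Afrezza, but not exceeding 24 units of Afrezza". The synopsis matches it.
- **Rule as a table.** Table 2 (Section 3.4.4) maps RAA to Afrezza as follows: under 4 U to 4 units; 4 and 5 to 8; 6 and 7 to 12; 8 and 9 to 16; 10 and 11 to 20; 12 U or more to 24. The lowest row has no lower bound. The blank cells beside 5, 7, 9 and 11 are read here as merged with the cell above.
- **Rule in the rationale.** Section 1.2 has the initial dose "multiplied by 2 and rounded down to the nearest Afrezza dose size, subject to Investigator discretion, but not exceeding 24 units of Afrezza".
- **Who is dosed.** Section 3.4.5 has every subject in the two Afrezza groups receiving Afrezza at Visit 2.
- **Product and meal.** Section 3.4.1: "Afrezza Inhalation Powder is a dry powder supplied as 4-, 8-, or 12-unit cartridges". Section 3.7.2.1: "The meal challenge will consist of 1-2 bottles of Boost nutritional shake (1 bottle is approximately 240 calories, 41 g carbohydrate". The protocol does not say which subjects take one bottle and which take two.

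**The concern.** This is the protocol's only numeric conversion from RAA to Afrezza. It governs the first exposure, at a ratio that Section 1.2 describes as well above the label's. For a subject with a small calculated RAA dose, the sentence and the table beneath it lead to different actions: no dose, or 4 units. Section 3.4.5 rules out the first, but nothing in the rule's wording yields the second. Two sites following the same protocol could therefore treat the same subject differently.

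Where 4 units is given to a subject whose RAA dose is below 2 U, the ratio exceeds the stated twofold conversion and the 1.5- to 2-fold range cited in Section 1.2. Section 1.3.1 lists both severe hypoglycemia and hyperglycemia from inadequate conversion as identified risks, so an unclear conversion matters in either direction.

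The discretion wording adds to this. If Section 1.2 governs, a different Visit 2 dose is permitted. If Section 3.4.4 governs, the same dose looks like a deviation. Section 3.4.4 brings in discretion over the Afrezza dose only after the meal challenge.

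**Working it through.** **Inputs.** The rule, the cap and Table 2 come from Section 3.4.4. Carbohydrate is 41 g per bottle, so 82 g for two (Section 3.7.2.1).

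**Formulas.** Text dose = min(24, 4 × floor(2 × RAA / 4)). RAA = grams of carbohydrate / grams covered by 1 U.

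**1. Reproduce Table 2 at whole units.**

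| RAA (U) | Text | Table 2 |
|---|---|---|
| 1 | 0 | 4 |
| 2, 3 | 4 | 4 |
| 4, 5 | 8 | 8 |
| 6, 7 | 12 | 12 |
| 8, 9 | 16 | 16 |
| 10, 11 | 20 | 20 |
| 12 or more | 24 | 24 |

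The rule reproduces the table at every whole-unit dose from 2 U up. It fails only below 2 U.

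**2. The range below 2 U.** If RAA < 2, then 2 × RAA < 4, floor(2 × RAA / 4) = 0, and the text dose is 0. Table 2 gives 4. The ratio of the table dose to the RAA dose is 4 / 1.9 = 2.11 at 1.9 U, 4 / 1.5 = 2.67 at 1.5 U, and 4 / 1.0 = 4.0 at 1.0 U.

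**3. When it occurs.** RAA < 2 requires each unit to cover more than 41 / 2 = 20.5 g with one bottle, or more than 82 / 2 = 41 g with two. Illustrative ratios (assumed, since the documents give none):

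| I:CHO | RAA, one bottle | Text / Table 2 | RAA, two bottles | Text / Table 2 |
|---|---|---|---|---|
| 1:20 | 41/20 = 2.05 | 4 / 4 | 82/20 = 4.10 | 8 / row for 4: 8 |
| 1:25 | 41/25 = 1.64 | 0 / 4 | 82/25 = 3.28 | 4 / 4 |
| 1:41 | 41/41 = 1.00 | 0 / 4 | 82/41 = 2.00 | 4 / 4 |

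The same subject at 1:25 meets the contradiction with one bottle and not with two.

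**4. Fractional doses between 4 and 12 U.** Table 2 has whole-unit rows only. Take 41 g at 1:7, or 82 g at 1:14: RAA = 5.86 U. The text gives 2 × 5.86 = 11.72, rounded down to 8. Reading 5.86 in the row for 5 also gives 8. Rounding it to the nearest unit and using the row for 6 gives 12, which is 4 units or 4 / 8 = 50% more. The same convention gives 16 against 12 (+33%) for 7.50 to 7.99 U, and 20 against 16 (+25%) for 9.50 to 9.99 U. If the RAA dose is rounded down, text and table agree at every value from 2 U up.

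**5. Discretion.** Section 1.2 attaches investigator discretion to the initial dose. The rule in the synopsis, Section 3.1 and Section 3.4.4 does not.

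**The case against.** **Zero is not a dose.** The smallest cartridge is 4 units and Section 3.4.5 has everyone in the Afrezza groups dosed, so Table 2 can be read as supplying an unstated floor. That reading is reasonable, and the documents taken together do not support withholding treatment. The reader must still infer it. No sentence states a minimum, and a floor of 4 units gives more than the stated twofold conversion.

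**The table is only illustrative.** Its note says the required dose "may differ from the examples provided in this table". That note concerns the total mealtime dose during the study. The table's title and its footnote are about the starting dose, so this does not settle Visit 2.

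**Fractions are not a true conflict.** This largely stands. No section calls for nearest-unit rounding, and the only direction that the protocol gives is down. A reader might infer that fractional doses can double between text and table, by moving 3.50 to 3.99 U up to the row for 4. The documents do not support that: those values sit in the printed row for doses under 4 U, which gives 4 units, as the text does. Likewise the 24-unit row begins at 12 U, so values just below 12 do not reach it as printed. What is left is a missing instruction.

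**Dose size against 4-unit step.** The rationale's wording and the 4-unit step coincide, because combinations of 4-, 8- and 12-unit cartridges are multiples of 4. There is no discrepancy there.

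**Consequences are contained.** This stands. It is one dose, given with two hours of clinical supervision, glucose measured to 120 minutes and glucagon available (Section 3.7.2.1), followed by titration.

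**Conclusion.** The point holds in a narrow form. For calculated RAA doses below 2 U the literal text gives 0 units and Table 2 gives 4, and Section 3.4.5 is inconsistent with the 0. From 2 U upward, text and table agree at every whole unit.

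Two secondary points hold. Fractional RAA doses between 4 and 12 U have no explicit row, which could shift a dose by one 4-unit step (at most +50%), and only if a site applies a rounding that the protocol does not state. Investigator discretion over the initial dose appears in Section 1.2 and is absent from the rule elsewhere.

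The result assumes that the blank Table 2 cells are merged and that rounding down is taken literally. How many subjects fall below 2 U cannot be estimated: the documents give neither an I:CHO distribution nor a rule for one bottle against two. It would be wrong to infer a widespread conflict or a doubling of doses. This is a safety-wording defect limited to one supervised dose; it is worth correcting because the correction is cheap.

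**What to change.** Reconcile the synopsis, Sections 1.2, 3.1, 3.4.4 and 3.4.5, and Table 2, so that one rule gives one outcome for every calculated RAA value:

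- State in words the outcome for values below 2 U, and make Table 2 and Section 3.4.5 match it.
- Rewrite the left column of Table 2 as contiguous ranges consistent with the text, so that no fractional value is without a row and no rounding convention has to be guessed.
- Say in one place whether investigator discretion applies to the Visit 2 dose.

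The sponsor decides which dose and rule are intended; none is proposed here. The cost is protocol wording and one table. No procedure, visit or analysis changes, and the statistical sections of the SAP contain no dosing rule to amend.

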#### 3.4.5 Treatment Assignment

Subjects in this study will be assigned a unique subject ID. Once screening procedures are complete and eligibility is confirmed, eligible subjects will be enrolled and randomized to treatment at Visit 2.

All subjects in the Afrezza groups will receive Afrezza at Visit 2 and continue this treatment through Visit 14. Subjects in the AID Control group will not receive Afrezza and will continue using their CSII pump with AID algorithm and RAA throughout the study.

#### 3.4.6 Drug Packaging and Blinding

This is an open-label clinical study. Neither clinical site personnel nor subjects will be blinded to treatment.

Confidential Page 32 of 70

\*The initial mealtime dose (taken at Visit 2 in the Afrezza + AID and Afrezza + Insulin Degludec groups) should not exceed 24 units of Afrezza.

#### 3.4.7 Drug Inventory and Accountability

The Investigator or designee is responsible for maintaining Afrezza and inhaler accountability records to ensure appropriate distribution throughout the clinical study. The Investigator should maintain records that document adequately that the subjects were provided the doses specified by the protocol and reconcile all Afrezza and inhalers received at the site before final disposition. At the end of the study, or as directed, all Afrezza and inhalers, including unused, partially used, and empty containers will be discarded.

#### 3.4.8 Treatment Compliance

It is expected that subjects will be compliant with all dosing instructions and subjects will administer the initial dose of Afrezza under clinical supervision at the study site.

#### 3.4.9 Prior and Concomitant Illnesses and Treatments

#### 3.4.9.1 Prior and Concomitant Illnesses

All illnesses present at screening will be considered to be prior illnesses (medical history). The subject's history of diabetes should be recorded at screening on the CRF. Subjects will also be questioned about drug and environmental allergies, family pulmonary disease history, and their smoking status/exposure to pulmonary toxins. The Investigator (or their designee) should document all other significant illnesses that the subject has experienced within 6 months of screening as medical history on the CRF.

After enrollment, any new or worsening illnesses should be documented as AEs on the CRF.

#### 3.4.9.2 Concomitant Treatments

Any medication or therapy that is taken by or administered to the subject during the course of the study must be recorded in the CRF. The entry must include the dose, regimen, route, indication, and dates of use.

Concomitant treatments, defined as treatments taken after enrollment, include all nonstudy treatments that are taken by subjects at any time during the clinical study, including prescription drugs, herbal supplements, or over-the-counter medications, should be recorded as concomitant medications.

Antiadrenergic drugs (e.g., beta blockers and clonidine) are prohibited during the study. Subjects should continue their prestudy antihyperglycemic medications but no changes to their medications should be made between Visits 1 and 2. The initiation of drugs or herbal preparations known to modify glucose metabolism that may, in the opinion of the Investigator, interfere with the clinical study results should be discussed with the medical monitor.

